3.1 STUDY OUTCOME MEASURES

The primary endpoint will be the detection of atrial fibrillation with a one-off ECG. The diagnostic yield of the machine learning algorithm will be analysed.

The diagnostic yield for AF detection of each health technology will be analysed. The time to first detection of AF will also be measured for each health technology.

Selective analysis will be performed looking at diagnostic yield for AF detection for different rhythm monitoring strategies which vary in frequency and duration.

4. PARTICIPANT ELIGIBILITY CRITERIA

Prospective participants will only be recruited from the high-risk AF population identified by the machine learning algorithm. They will need to fulfil the inclusion criteria in order to enrol into the study.

4.1 INCLUSION CRITERIA

To take part in the study, participants must meet all the following requirements:

- a) Aged 18 years old and above
- b) Identified as high-risk for AF by our machine learning algorithm

c) Access to smartphone if part of Photoplethysmography or long term AliveCormonitoring groups

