SAMPLE SIZE ~ 9 000 high risk AF patients identified from machine learning algorithm

~ 1 800 patients for further AF screening

ELIGIBILITY Inclusion criteria

Aged 18 years old or above

Identified as high-risk for AF by our machine learning algorithm

Access to smartphone depending on allocated screening group

Exclusion criteria

Have already a diagnosis of atrial fibrillation prior to study enrolment

Below the age of 18 years old

Presence of cardiac electronic implantable device

DURATION 1.5 years

STUDY FLOW CHART

[figure not shown]

Figure 1 Study Design

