2. STUDY OBJECTIVES

AIMS

- 1. To evaluate the potential benefit of using our machine learning algorithm to aid AF screening
- 2. To compare the use of different health technologies for AF screening
- 3. To evaluate the optimal duration and frequency of rhythm monitoring for AF screening

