3. STUDY DESIGN

This will be a 1.5-year study in which participants will be recruited prospectively from databases of 46 general practices (GPs) in the Hounslow area. Our machine learning algorithm will be used on these databases to identify our participants. Our participants will be identified as those at risk of developing atrial fibrillation. The practices will be cluster randomised into 4 groups. The high- risk AF individuals will be invited for screening for AMLA-AF protocol, version 1.1 25/10/21, IRAS Project ID: 293493

AF. The four groups are as follows: (1) ECG group (2) Holter monitoring group, (3) a Photoplethysmography (PPG) monitoring group and (4) a long term AliveCor monitoring group.

All individuals who have agreed to participate in the study will be screened initially once with a single lead ECG recording using an AliveCor device. This will be done either at their general practice or a research clinic at West Middlesex University Hospital. Any individual found to have AF will be followed up by their general practice to receive appropriate treatment. They will also not be required to have any further screening.

After this initial screening, if an individual has not been found to have AF and belongs to groups 2-4, they will undergo further screening for a period of 3 months. This will be based on their allocated group. They will be able to take their screening technology home. Again, if any individual is found to have AF, they will be followed up by their general practice to receive appropriate treatment.

Participation in this study will be entirely voluntary and will not affect participants' current or future care. Participants will be free to withdraw from the study at any time without having to provide a reason. Participants will be recruited prospectively from general practices, on a first-come first-serve basis, to minimise bias. Recruitment will continue throughout the study.

Data collected from participants prior to drop out or loss to follow-up will be included in the data analysis. We are not aware of any ongoing studies that are competing for the same group of participants or whose results may affect recruitment. Similarly, our study will not jeopardise other studies either.

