5. STUDY PROCEDURES AND RANDOMISATION

Prior to patient recruitment, the machine learning algorithm will be run centrally at NHS Hounslow Clinical Commissioning Group, Hounslow House. It will be run across 46 general practice databases in the Hounslow area, which includes an estimated population of 315 000 people.

The algorithm will generate an anonymised list of high- risk AF individuals with their associated general practice. It is expected that this will be approximately 9 000 people.

Each general practice will be clustered into three different sets depending on the size of the population of high- risk AF patients found at that practice. The sets are classed into large (>200 patients identified screen), medium (100-200 patients) and small (< 100 patients). This will allow the GP practices to be later cluster randomised into four groups corresponding to the different screening strategies, with roughly equal number of large/medium/small GP practices in each group. These four groups that we will compare are: (1) ECG group, (2) holter monitoring group, (3) a PPG monitoring group and (4) a long term AliveCor monitoring group.

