7. SCREENING AND FOLLOWUP

Participants' care will continue under their normal clinical or healthcare teams. Therefore, their followup will be arranged by and conducted by these team(s).

Following recruitment into the study, each participant will be invited for screening for AF at their practice or a research clinic at West Middlesex University Hospital.

At the baseline assessment, each participant will be required to have a single lead ECG recording for a minimum of 30 seconds using an AliveCor device (two metal pads on a plastic strip, Figure 2) and smartphone which will be provided by the research team. Figure 3 demonstrates the use of the device with a smartphone. For a recording, at least 1 finger is required to rest on each of the metal pad (electrodes). If AF is identified from this recording, the patient will be referred back to their practice for appropriate treatment.

Figure 2: AliveCor device

[figure not shown]

Figure 3: AliveCor recording

Participants without a diagnosis of AF in the holter monitoring group, photoplethysmography (PPG) monitoring group and the long term AliveCor monitoring group will be given a health technology to take away. They will have monitored with this technology for 3 months. The technology that they receive will be based on the monitoring group they belong to. The ECG group will not have any further monitoring.

For the holter monitoring group, the participants will receive a 72-hr holter monitor/ECG patch initially, and two further 24-hr holter monitors/ ECG patches at 6 and 12 weeks. These will be returned to the research team following completion of each monitoring period.

For the Photoplethysmography (PPG) monitoring group, the participants will be given access to a smartphone application called Fibricheck to use on their own smartphone. The participant will be provided with a QR code to scan for the prescription of 3- month

monitoring period. The participant will need to download the Fibricheck App on their own smartphone from the App store. They will then need to scan the QR code with the Fibricheck App. The participant will then be able to start making recordings by placing their finger on the camera for 1 minute. Figure 4 demonstrates how to set the Fibricheck App on a smartphone and Figure 5 shows how to take a recording with the App.

[figure not shown]

Figure 4: How to set up Fibricheck App on smartphone

[figure not shown]

Figure 5: How to take a recording using the Fibricheck App

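### Smartphone access is an entry criterion in only two of the four randomised groups, so comparing either smartphone technology with ECG or Holter compares differently selected populations

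*Protocol*

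**What the plan says.** Section 3 of the protocol states: "The practices will be cluster randomised into 4 groups". Section 5 balances the allocation on practice size only, "with roughly equal number of large/medium/small GP practices in each group". Individuals are then recruited at the allocated practices.

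Section 4.1 says that "participants must meet all the following requirements", and the third requirement is "Access to smartphone if part of Photoplethysmography or long term AliveCormonitoring groups". The Study Summary repeats the rule: "Access to smartphone depending on allocated screening group". Section 7 shows that the rule has practical force, because the PPG and long-term AliveCor groups both run their app on the participant's own phone for three months. The ECG and Holter groups have no corresponding criterion. For the baseline ECG, which every group has, the device is used with a "smartphone which will be provided by the research team".

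Aim 2 in Section 2 is "To compare the use of different health technologies for AF screening". Section 3.1 adds "The diagnostic yield for AF detection of each health technology will be analysed", together with time to first detection for each technology.

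**The concern.** The third criterion can be applied only once a practice's group is known, so who may enter depends on the allocation. Randomising practices balances the lists of high-risk patients in expectation. It does not balance the people enrolled from those lists when two groups filter on smartphone access and two do not. Practice size, the only balancing factor, does nothing about this.

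If smartphone access is related to the risk of AF (through age, for example), the underlying yield of the smartphone groups will differ from that of the ECG and Holter groups even when the technologies detect AF equally well. A difference between PPG and Holter, or the lack of one, could not then be attributed to the technology. Cross-type contrasts of this kind are a substantial part of what Aim 2 sets out to learn.

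**Working it through.** **The plan's own figure.** Section 8 expects 9 000 × 20% = 1 800 participants, which reproduces. Section 8 gives no power calculation to reproduce, and the point does not depend on one.

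**Who can enter which group.**

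| High-risk patient | ECG | Holter | PPG | Long-term AliveCor |
|---|---|---|---|---|
| With smartphone access | yes | yes | yes | yes |
| Without smartphone access | yes | yes | no | no |

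Of the six pairwise contrasts, four cross the line: PPG–ECG, PPG–Holter, AliveCor–ECG and AliveCor–Holter. The other two, PPG–AliveCor and ECG–Holter, apply the same rule on both sides.

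**Possible size (assumed inputs).** The protocol gives neither the share with smartphone access nor AF rates by access. Suppose that half the high-risk list is older and half younger, with AF yields a1 and a2 and ownership o1 and o2, and that all technologies detect AF equally well.

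- Unrestricted groups: 0.5·a1 + 0.5·a2
- Smartphone groups: (0.5·o1·a1 + 0.5·o2·a2) / (0.5·o1 + 0.5·o2)

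| a1, a2 | o1, o2 | Unrestricted | Smartphone groups | Relative difference |
|---|---|---|---|---|
| 12%, 6% | 70%, 95% | 9.0% | (4.20 + 2.85)/0.825 = 8.5% | −5% |
| 12%, 6% | 50%, 90% | 9.0% | (3.00 + 2.70)/0.70 = 8.1% | −10% |
| 16%, 5% | 30%, 90% | 10.5% | (2.40 + 2.25)/0.60 = 7.8% | −26% |
| a1 = a2, or o1 = o2 | any | same | same | 0 |

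**Cross-check without age classes.** Take the overall yield p = 1/9 = 11.1%, from the number needed to screen of 9 in Section 1. Let s be the share with access and r the AF rate ratio, people with access against people without (both assumed). The yield among those with access is p·r / (s·r + 1 − s).

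- s = 0.9, r = 0.85: 11.1% × 0.85/0.865 = 10.9% (ratio 0.98)
- s = 0.7, r = 0.7: 11.1% × 0.70/0.79 = 9.8% (ratio 0.89)
- s = 0.5, r = 0.5, the extreme corner: 11.1% × 0.50/0.75 = 7.4% (ratio 0.67)
- r = 1: 11.1%, no bias

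If r exceeded 1, the sign would reverse.

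**Limit of both calculations.** They use a single overall yield. In groups 2 to 4, monitoring follows only a baseline ECG without AF, so the added yield from monitoring is a different quantity. The calculations show how the selection works; they do not forecast the result.

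**The case against.** The strongest reply concerns reach. The primary endpoint is AF on a one-off ECG, recorded in every group with the same type of device and a phone supplied by the research team. It is not a technology contrast, so the criterion cannot confound it as one; it can only change who contributes to the pooled yield. PPG versus long-term AliveCor, the direct comparison of two mobile technologies, applies the same criterion on both sides. ECG versus Holter is likewise unaffected. The comparisons of monitoring duration and frequency are made within a group and keep their internal validity. All of this stands. A reader might infer from the eligibility rule that every technology comparison, or the primary result, is compromised, and the protocol does not support that.

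The size and sign are also assumed. Everyone enrolled has already been selected as high-risk by the algorithm, which may weaken any link between age and AF. The protocol does not show that people without smartphones have more AF. This stands too, and limits what can be said about magnitude.

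A third reply is that a statistical analysis plan, not seen here, may define the comparison population and any adjustment. That is fair, and the protocol's silence on those matters is not the point. But such a plan can restrict to people with access only if access was recorded in the ECG and Holter groups, and nothing in the protocol says that it will be.

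A last reply is that the trial compares pragmatic strategies, in which smartphone access is part of the strategy. In that case people without a smartphone would have to stay in the PPG and AliveCor denominators as not screened. Section 4.1 excludes them, so that comparison is not obtained either.

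**Conclusion.** The point holds for the four cross-type contrasts under Aim 2, PPG or long-term AliveCor against ECG or Holter. Eligibility differs by allocated group, and randomisation does not protect these contrasts. This rests on the protocol's text and on no assumption.

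The effect on AF yield does rest on assumptions. In the age-mix scenarios it runs from none to about a quarter lower relative yield in the smartphone groups, and the extreme corner of the cross-check reaches a third. It would be tempting to conclude that the smartphone groups will show lower yield. The documents do not establish even the direction, and if access is unrelated to AF risk there is no bias.

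This should be fixed before recruitment data are relied on for Aim 2. It is not a threat to the primary endpoint or to Aim 3.

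**What to change.** Record smartphone access (yes/no) at enrolment in all four groups, using the same definition that decides entry to the PPG and long-term AliveCor groups. State in the protocol that comparisons of PPG or long-term AliveCor with ECG or Holter are made among participants with access in every group. Keep all ECG and Holter participants for the one-off ECG yield and for the within-group analyses. The difference due to this criterion is then zero by construction.

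The change costs one enrolment question and one sentence. It also leaves fewer ECG and Holter participants in the cross-type comparisons. Assuming an equal split of 1 800/4 = 450 per group and the average ownership in the three age-mix scenarios (82.5%, 70%, 60%), about 371, 315 or 270 per group would remain. The result would apply only to people with smartphone access.

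Requiring a smartphone in all four groups would also equalise eligibility, but it would remove people without one from the primary endpoint and from Aim 1, so it is not recommended. The restriction does not address the separate rule in Section 4.3 that withdraws participants who cannot use their allocated technology.

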4.2 EXCLUSION CRITERIA

Participants with any of the following will not be able to take part in the study:

- a) Have already a diagnosis of atrial fibrillation prior to study enrolment
- b) Below the age of 18 years old
- c) Presence of cardiac electronic implantable device

4.3 WITHDRAWAL CRITERIA

Participants will be withdrawn from the study if they fulfil one of the following:

- a) Unable to use their screening health technology
- b) Withdrawal of consent
- c) Presence of cardiac electronic implantable device

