5.1 RECRUITMENT

Following this, each general practice will be visited separately and the algorithm will be run at each individual practice to identify individual high-risk AF patients. A member of each general practice will be shown how to run the algorithm and will run it on the database of the general practice. High-risk AF participants will be invited to be recruited into the study by a member of the general practice team. Every effort will be made to recruit vulnerable adults who lack capacity so they can be recruited if they wish to be involved. All high -risk participants recruited will be registered and flagged up on a depersonalised health data set covering the North West London (NWL) population, known as the Discover dataset, which is the NWL health research cohort register. This will allow the retrieval of health care data of these participants while keeping their anonymity. Each participant will have an anonymous identifier number. Approval for this has been sought from NWL Data Access Committee.

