8. STATISTICS AND DATA ANALYSIS

It is estimated that 9 000 participants will be identified to be high risk for AF. Taking into account the dropout from previous screening exercises, we estimate that 1 800 (20%) participants will belong to the four groups.

The diagnostic yield for AF detection will be analysed for the machine learning algorithm and each health technology.

There will be selective analysis of the data collected from the monitoring groups to determine the optimal frequency and duration.

For each participant for the holter monitoring group, two rhythm histories will be created. The first rhythm history will just include the results of 72hr monitor. The second rhythm history will include the results of first 24hrs of the 72hr monitor, the results of the second 24hr monitor and the third 24hr monitor. This will allow the screening strategies of 3 x24hr monitoring and 1 x 72hr monitoring to be compared. The diagnostic yield of AF detection for the two strategies will be compared.

The data from the PPG and long term AliveCor monitoring groups will then be selectively analysed with some recordings blanked from analysis to compare the diagnostic yield of different durations (1-month vs 3 months) and different frequencies (Daily vs alternate days vs weekly).

Data analysis will be performed at West Middlesex University Hospital.

All high-risk AF patients will be followed up for the detection of AF. This will be at least 1 year from the last recruited patient.

The end of the study will be defined as last followup required for the purposes of the study.

Data and all appropriate documentation will be stored for a minimum of 10 years after the completion of the study, including the follow-up period.

AMLA-AF protocol, version 1.1 25/10/21, IRAS Project ID: 293493

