9.2 CONSENT

A member of the general practice care team will approach prospective participants to offer participation in the study in the first instance.

Members of the research team will only make contact with prospective participants after a member of the clinical care team has introduced the option of partaking in this study to them.

Consent to enter the study will be sought from each participant only after a full explanation has been given, an information leaflet (patient information sheet) offered and time allowed for consideration. Signed written and verbal informed consent will be obtained from every participant/ witness/ relative at the beginning of the study at the point of enrolment. For vulnerable participants, every effort will be made to help their understanding of the study. We will also involve witnesses and/or relatives as necessary. Participants' suitability to partake will be checked prior to screening occurring after enrolment, according to inclusion and exclusion criteria. The right of the participant to refuse to participate or withdraw from the study at any point without giving reasons will be respected at all times.

After the participant has entered the study, their general practice clinician(s) remain free to give an alternative treatment or monitoring to that specified at the start of the research study, at any stage if they feel it is in the participant's best interest. The reasons for doing so will be recorded. In these cases, the participants can remain within the study for the purposes of data collection, follow-up and data analysis if they wish.

All participants are free to withdraw at any time from the study without giving reasons and without prejudicing current, further or future treatment.

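### Section 4.3(a) withdraws from the whole study anyone unable to use the allocated technology, which conflicts with the follow-up plan and puts the technology comparison at risk

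*Protocol*

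**What the plan says.** Section 4.3 opens with "Participants will be withdrawn from the study if they fulfil one of the following", and its item (a) is "Unable to use their screening health technology". The item stands beside withdrawal of consent and has the same consequence.

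Four other places bear on what happens to such a participant:

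- Section 3: "Data collected from participants prior to drop out or loss to follow-up will be included in the data analysis".
- Section 8: "All high-risk AF patients will be followed up for the detection of AF", for at least 1 year from the last recruited patient. No exception is made for withdrawn participants.
- Section 5.1 flags recruited participants on a linked regional dataset: "This will allow the retrieval of health care data of these participants while keeping their anonymity".
- Section 9.2 covers participants whose practice clinician changes their monitoring: "the participants can remain within the study for the purposes of data collection, follow-up and data analysis if they wish".

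On outcomes, section 3.1 states "The primary endpoint will be the detection of atrial fibrillation with a one-off ECG" and then "The diagnostic yield for AF detection of each health technology will be analysed". It adds time to first detection for each technology. It does not state the denominator of the yield.

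**The concern.** Aim 2 in section 2 is to compare the use of different technologies for AF screening. Whether people can use a technology is part of that comparison, so a participant who cannot is an unsuccessful use of the strategy. Section 4.3(a) turns that result into a departure from the study, after randomisation and for a reason tied to the allocated group.

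Two things are at stake. If these participants leave the denominator, yield describes only people able to use the device, and groups with more inability look better than they should. If they also leave follow-up, later AF becomes unknown in the people for whom the strategy failed. Time to first detection is exposed in the same way, because observation would end for a reason linked to the technology.

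**Working it through.** **1. Which groups the rule can reach (sections 4.1 and 7).**

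- ECG group: no monitoring after the baseline recording, so the rule cannot arise for take-home monitoring.
- Holter group: a worn monitor or patch, once for 72 hours and twice for 24 hours.
- PPG and long term AliveCor groups: participants operate an app on their own smartphone twice daily for 3 months.

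Exposure to the rule therefore differs by group. That it is greatest in the two app groups is an inference from these tasks. The protocol gives no rate for any group.

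**2. The sections side by side.**

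- Section 4.3 against section 8: one takes the participant out of the study; the other follows every high-risk patient for AF. The protocol does not say which prevails.
- Section 4.3 against section 9.2: a participant moved to other monitoring by the practice may stay for follow-up and analysis, while one who cannot work the device is withdrawn.
- Section 3 keeps data gathered before drop-out. Someone who never made a home recording has a baseline ECG but no technology data to keep.

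**3. The protocol's own figure.** Section 8 expects 20% of 9 000: 9 000 × 0.20 = 1 800, which reproduces. An equal split, which is an assumption, gives 1 800 / 4 = 450 per group. The protocol states no power, effect size or inability rate to check against.

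**4. Size of the possible distortion.** Let y be the yield among users and u the share withdrawn as unable, with no detection by the technology.

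- All allocated participants in the denominator: yield = y × (1 − u).
- Withdrawn participants removed: yield = y.
- Overstatement factor: y / [y × (1 − u)] = 1/(1 − u).

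For illustration take y = 1/9 = 11.1%, from the number needed to screen of 9 in section 1. That figure describes the algorithm, not a device, so using it here is an assumption. All values of u are assumed.

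| u | Users of 450 | Detections (users / 9) | Yield, all 450 | Yield, users only | Factor |
|---|---|---|---|---|---|
| 2% | 441 | 49 | 10.9% | 11.1% | 1.02 |
| 10% | 405 | 45 | 10.0% | 11.1% | 1.11 |
| 20% | 360 | 40 | 8.9% | 11.1% | 1.25 |
| 30% | 315 | 35 | 7.8% | 11.1% | 1.43 |

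The factor depends on neither the group size nor y.

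**5. Effect on a comparison.** Assume equal yield among users, u = 2% for Holter, and u = 10%, 20% or 30% for an app group. The Holter-to-app yield ratio with everyone counted is 0.98/0.90 = 1.09, 0.98/0.80 = 1.225 or 0.98/0.70 = 1.40. With the withdrawn removed, each would read 1.0.

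**The case against.** A reader might infer that the rule definitely flatters the smartphone technologies and definitely loses follow-up. The protocol does not support either reading.

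- **Denominator.** Nothing in the protocol removes withdrawn participants from the yield denominator. Section 3 keeps their earlier data, and everyone has a baseline ECG. Analysis sets are commonly left to a statistical analysis plan, so silence on the denominator is not itself a fault. This stands, and it makes the inflation conditional.
- **Follow-up.** Section 8 covers all high-risk patients and section 5.1 supplies a data route. Loss of follow-up is therefore not established; what is established is that sections 4.3 and 8 disagree.
- **Which groups.** No inability rates are given. Holter participants have three wearing periods and must return each device, so they can also be unable. The smartphone requirement in section 4.1 should screen out some of the people least able to use an app. The direction is plausible, not shown.
- **Scope.** The primary endpoint comes from a recording made at the baseline visit on equipment the research team provides, before any take-home device. It is largely untouched.

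The objection does not remove the rule itself. It is mandatory, it applies to the study and not just the device, and it depends on allocation. An analysis plan can define a denominator, but it cannot recover follow-up that was not collected because the protocol ended participation.

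**Conclusion.** The point holds as a badly framed withdrawal rule and a contradiction within the protocol, not as a demonstrated bias. Section 4.3(a) does not separate stopping the device from leaving the study, and it disagrees with section 8 on later follow-up.

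If withdrawn participants leave the denominator, a technology's yield is overstated by 1/(1 − u), which is 1.11 to 1.25 for an assumed u of 10% to 20%. If they stay in, there is no overstatement from this source. The calculation also assumes that those withdrawn contribute no detection by the technology. The outcomes at risk are the comparison of technologies and time to first detection. The change is worth making because it is cheap and prevents a possible bias that depends on group.

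**What to change.** Reword section 4.3(a) so that inability to use the technology ends use of the device only. State that the participant then:

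- remains in the study;
- stays in the yield denominator, counted as not detected by that technology;
- continues record-based AF follow-up through the linked dataset in section 5.1, unless consent is withdrawn.

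Reconcile sections 3, 4.3, 8 and 9.2 so that they say the same thing about retention, follow-up and analysis. Reporting the number unable to use each technology, by group, would be a useful addition, but its absence is not an error.

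The cost is a short protocol amendment. No visits are added, because the follow-up is from records. The downside is slightly lower reported yields where inability is common.
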